# 3 EVALUATION PRODUCT(S)

# 3.1 DESCRIPTION OF EVALUATION PRODUCT(S)

Avance® Solo will include the collective description for a complete device capable of delivering negative pressure to the incision site and managing exudate generated by the incision. It comprises:

"This investigation pertains to Avance®Solo, a single use battery powered negative pressure system, with Mölnlycke as the legal manufacturer with its headquarter located in Gothenburg, Sweden. Avance®Solo consists of different products that are FDA compliant, which together form a system for wound management via the application of negative pressure (Figure 2). Avance®Solo maintains negative pressure nominally at -125 mmHg on low and moderately exuding wounds. The pump is pocket sized and can be carried in a pocket or attached to a belt with a belt clip that is assembled with the pump. To maintain the pressure, there is a recycling sound. To reduce the sound of cycling, a night case can be used to facilitate comfort during sleep."

A proprietary Controlled Fluid Management (CFM) technology, the Avance® Solo single use negative pressure system shares fluid management between an absorptive multi-layered dressing and a 50ml canister, reducing the potential for dressing saturation. This technology is theoretically designed to reduce the potential loss of therapy arising from dressing saturation.

 The addition of a canister to the absorptive dressing ensure the dressing does not become overwhelmed with draining and therapy will continue to be delivered regardless of dressing saturation

- Sharing fluid management between an absorptive dressing and canister can reduce the frequency of dressing changes
- Avance® Solo NPWT system continues to deliver negative pressure to the wound site, even with low to moderate amounts of fluid saturation in the dressing
- Avance® Solo features both audible and visual alarms so therapy can be restored in an efficient timely manner
- Avance Solo Border dressings Safetac® adhesive has been proven to minimise trauma to wound site and surrounding skin upon dressing removal
- -125mmHg continuous negative pressure

The pump is a controllable vacuum pump apparatus, which can be left to operate automatically, delivering continuous negative pressure (nominally -125mmHg) to the incision site. The pump's lifetime is 14 days and is powered with 2 lithium batteries specific to the pump. Batteries shall be replaced once pump alarms for Low battery or after 7 days.

The control product (HAAMPOD) has not undergone any prospective randomized controlled trial. (Optifoam® Gentle Post-Op). It has been deemed equivalent and acceptable therapy for the Mount Sinai West Operating room, by equivalency data by the Mount Sinai purchasing group.

#### **Precautions:**

The use of anticoagulants does not deem a patient inappropriate for treatment with the Avance® Solo, however, haemostasis must be achieved before applying the dressing and continued frequent assessment must be maintained and considered throughout the therapy.

Avance® Solo must not be placed over exposed arteries, veins or organs. Greater care should be taken with respect to weakened, irradiated or sutured blood vessels or organs.

Avance® Solo is contraindicated for patients with malignancy in the incision site or margins of the incision (except in palliative care to enhance quality of life), previously confirmed and untreated osteomyelitis, non-enteric and unexplored fistulaes, sinus tracts and areas of tunnelling or necrotic tissue with eschar or exposed anastomotic sites, use over exposed blood vessels, nerves or organs or use on exposed bone or tendon unless a non-adherent dressing is used to protect the exposed areas.

Avance® Solo is registered in the country of use (CE marked for Europe and 510k approved for the US).

A number of different dressing sizes are produced by the sponsor, Molnlycke (shown in Table 1).

Table 1: Molnlycke dressing sizes

Dress	ing size	Effective pad size	Pad Area (cm²)
Document Number:	1	Document Part:	000
Document Version:	01	Document Status:	Released

10cm x 20cm	5cm x 15cm	75
10cm x 30cm	5cm x 25cm	125
10cm x 35cm	5cm x 30cm	150
15cm x 15cm	10cm x 10cm	100
15cm x 20cm	10cm x 15cm	150
15cm x 30cm	10cm x 25cm	250
20cm x 20cm	15cm x 15cm	225
25cm x 25cm	20cm x 20cm	400

The dressing and pad sizes that will be used for the closed incision wounds in this study are listed below (shown in Table 2).

Table 2: Dressing sizes to be used in the study

Dressing size	Effective pad size	Pad Area (cm²)
10cm x 20cm	5cm x 15cm	75
10cm x 30cm	5cm x 25cm	125
10cm x 35cm	5cm x 30cm	150
15cm x 20 cm	10cm x 15cm	150
15cm x 30cm	10cm x 25cm	250

3.2 OPTIFOAM® GENTLE POST-OP – (MEDLINE IN, NORTHFIELD IL) – IS A "SILICONE FACED AND BORDERED POST OPERATIVE FOAM AND SUPERABSORBENT CORE AND FLEXIBLE DESIGN." (PER PACKAGE INSERT) THIS PRODUCT IS DEEMED ADEQUATE FOR HIGH RISK SURGICAL INCISIONS PER MOUNT SINAI VALUE ANALYSIS/ (NOT SUBJECT TO IRB APPROVAL NOR REVIEW)/PURCHASING. WHICH WILL BE KEPT IN PLACE FOR UP TO 7 DAYS (PER PACKAGE INSERT), ALTHOUGH DRESSING CHANGES UP TO 4 PER 14 DAYS WILL BE ALLOWED. \*NOTE THIS PRODUCT IS SUBJECT TO CHANGE BASED UPON MOUNT SINAI PURCHASING CONTRACTS.

Dressing size	Effective pad size	Pad Area (cm²)
10.2 x 20.3 cm	5.1 cm x 15.2 cm	77.5
10.2 x 25.4 cm	5.1 cm x 20.3 cm	103.5
10.2 x 30.5 cm	5.1 cm x 25.4 cm	129.5

# a. PACKAGING AND LABELLING

2. All evaluation products will be supplied in standard packaging. No additional labelling will be appended to the evaluation products.

#### a. METHOD OF DISTRIBUTION

3. Delivery of product and will be arranged and agreement between Molnlycke and the center.

# 3.3 RECONCILIATION

All evaluation products, which have not been used by the end of the evaluation, must be returned to Molnlycke. The clinician will maintain an inventory, which will include details of receipt, use and return of all evaluation products (Appendix 1). The control product will be managed by the Mount Sinai West operating room product acquisition supply system.

#### 4 EVALUATION PATIENT POPULATION

# 4.1 NUMBER OF PATIENTS

30 patients in each arm meeting the inclusion criteria

#### 4.2 PATIENT SOURCES

Patients will be recruited from the Mount Sinai West Hospital general (includes Plastic surgery as a Division of Plastic Surgery) and orthopedic surgery practices of foot and ankle surgery, vascular surgery, general surgery, and Plastic surgery. These practices have a similar location for outpatient follow-up of New York New York, 10019. USA.

# 4.3 SELECTION CRITERIA

Patients with an incision deemed suitable for treatment with Avance® Solo or HAAMPOD will be screened against the inclusion and exclusion criteria. Only patients who meet the eligibility criteria will be included in the evaluation. For patients with more than one incision, only the largest or most suitable of their incisions will be included in the evaluation and will need to be in line with the instructions for use and contraindication instructions and will be an incision which fits the dressing sizes included.

Only 1 dressing per incision must be used on an incision and this incision will be referred to as the reference incision. Any other incisions the patient may have will be treated in accordance with standard local procedures. The 1st dressing will be placed immediately upon completion of the operation

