#### 2 EVALUATION DESIGN

# 2.1 EVALUATION DESIGN

Open label, two armed, prospective, single center, quality equivalency assessment.

Immediate post operative application of Avance® Solo Negative pressure wound therapy on "high risk" closed surgical incisions. Versus the hospital best clinical practice dressing HAAMPOD. (Please note there is no prospective clinical data driven data, the hospital purchasing department develops and indicates the brand based upon cost).

The patient will be undergoing:

- Foot and ankle surgery
- Vascular groin incision, vascular axillary incisions
- Long leg vein harvest incision
- Closed forefoot and major amputation surgery
- Possibly: breast augmentation and reduction surgery

\*Note: The surgical indication is chosen based upon previously published data of high risk incisions. (It is beyond the scope of a protocol to educate the IRB in regards to the full definitions of high risk surgical inicisions)

Patients will participate in the study for 4 applications or up to 2 weeks treatment, whichever comes first. During this time clinicians will be asked to complete questions pertaining to the incision and to the performance and overall acceptability of Avance®Solo or the HAAMPOD.

Throughout the evaluation patients will be treated according to the product instructions for use for either product.

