#### 4.3.1 Inclusion Criteria

The following criteria must be met before a patient is recruited to the evaluation:

- The patient must be at least 18 years of age
- Males and females provided they are not pregnant and if of reproductive age are using contraception.
- Have a closed surgical incision post-surgery/closure (<24 hours after).
- The patient is able to understand the evaluation and is willing to consent to the evaluation.
- Undergoing appropriate: wound "high risk" surgery
- Foot and ankle surgery
- Vascular groin incision
- Long leg vein harvest incision
- · Closed forefoot and major amputation surgery
- Breast augmentation and reduction surgery
- Patient on metabolic agent, immunosuppressants, or steroid therapy will not be excluded from this study

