# 4.3.2 Exclusion Criteria

- Incisions in excess of effective dressing pad size provided.
- Patients with a known history of poor compliance with medical treatment.
- Patients who have participated in this trial previously and who were withdrawn.
- Patients with known allergies to product components (silicone adhesives and polyurethane films (direct contact with incision), acrylic adhesives (direct contact with skin), polyethylene fabrics and super-absorbent powders (polyacrylates) (within the dressing).
- Incisions where daily inspection is required underneath the dressing.
- Incisions which have an infection which is not being treated with systemic antibiotics.
- Incisions which are actively bleeding.
- Exposure of blood vessels, organs, bone or tendon at the base of the reference incision.

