# At baseline assessment the following parameters will be requested prior to application of dressings:

- Treatment setting (Operating room/hospital bed)
- Dressing routinely used (Foam, Film, non-woven, hydrocolloid, alginate, other)
- Patient demographics (Age, gender)
- Size of dressing used Type of surgery Date of surgery
- Location of surgical incision site (Left or right side, head/neck, chest, back, abdomen, retroperitoneal, groin, upper or lower arm, upper or lower leg, other)
- Risk factors for a surgical incision healing complication (obesity, smoker, low vascularity, diabetes, radiotherapy, immuno-compromised patient, or other)
- Length of incision (cm)
- Method of closure (Sutures, staples, tissue adhesive/glues, skin closure tape, other)
- Exudate level (None, slight, moderate, heavy)
- Drain present (yes/no)
- Condition of surrounding skin (Healthy, inflamed, macerated, dry and flaky, other)
- Assessment of infection (yes/no)
- Any incision complications and / or clinical signs of infection present (None, incision site static or deteriorating, dehiscence, increased exudate/secretion levels, increased pain, increased temperature around the wound, discolouration of granulation tissue, friable granulation, tissue necrosis, local erythema, oedema, purulent drainage, odour, other)

Photographs (yes/no)

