#### 8 STATISTICAL CONSIDERATIONS

A Chi squared evaluation of the data will be carried out in regard to the dichotomous yes/ no variable of post operative wound complication of not. The two groups will be randomized based upon a computer generated randomization schedule. Due to the small numbers the randomization will not be controlled for the surgical type.

Based upon the current literature the expected wound complication rate of the associated wound complication rate would be 16% (or 5/30), based upon best treatment effect of NPWTi the rate of wound complication would be 8% or (2/30). While this is a clinically significant and cost significant difference, in order to show a statistically significant difference at these levels, with an P $\beta$  of 0.8 and a P $\alpha$  of 0.05, the study would have to enroll a cohort of 324 patient with 162 patients in each. To date no study of post operative wound dressings has approached this level of statistical validity. Prior to embarking on any such study, a pilot study such as this needs to be undertaken to validate the basic assumptions.

Cost analysis of post operative wound complications will not be collected as a portion of this data, although LOS and freedom from readmission will be assessed. The data set is seen as exploratory and is not powered to find statistical significance.

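### The plan does not say when the arm is opened or that it is concealed, so the surgeon could know it while eligibility, reference incision, closure method and drain use are still open

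*Combined protocol and SAP*

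**What the plan says.** All references are to the combined protocol and SAP.

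- **Design (2.1).** "Open label, two armed, prospective, single center, quality equivalency assessment". The same section plans "Immediate post operative application of Avance® Solo Negative pressure wound therapy".
- **Allocation (8).** "The two groups will be randomized based upon a computer generated randomization schedule". The section adds that surgical type will not be controlled for. It gives no time of assignment, no holder of the schedule and no concealment.
- **Sequence (5.1).** Consent and the eligibility checklist stand in the pre-trial row, ahead of the first dressing on Day 0.
- **First dressing and reference incision (4.3).** "The 1st dressing will be placed immediately upon completion of the operation". For patients with several incisions, "only the largest or most suitable of their incisions will be included in the evaluation". Only one dressing may be used on an incision.
- **Inclusion (4.3.1).** Among the criteria to be met before recruitment: "Have a closed surgical incision post-surgery/closure (<24 hours after".
- **Exclusion (4.3.2).** Incisions larger than the pad, "Incisions which are actively bleeding", and incisions with exposed vessels, organs, bone or tendon.
- **Baseline data (6.1).** Incision length, method of closure and "Drain present (yes/no" are recorded before the dressing goes on. The treatment setting may be the operating room or a hospital bed.

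**The concern.** Several decisions that define who is in the trial, and how the wound is treated apart from the dressing, are made during the operation or at its end. If the surgeon knows the arm by then, those decisions can follow it. In an open-label trial, the safeguard is to keep the arm closed until they are final. This plan does not provide that safeguard.

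Two things would be at stake. First, patients could be kept or dropped, or one incision preferred to another, according to the arm, so that the arms are no longer comparable at entry. Second, closure method and drains plausibly bear on outcomes that the primary composite in Section 1.2 counts: dehiscence, incomplete closure at 7 days and persistent drainage. If they differ by arm because the arm was known, the comparison is no longer of dressings alone. The plan itself offers a reason why they might: Section 1.1 credits negative pressure with removing drainage and reducing seroma and haematoma, and a surgeon who accepts this could decide differently about a drain.

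**Working it through.** **1. What fixes the moment of allocation?**

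| Section | What it fixes | Does it time the allocation? |
|---|---|---|
| 2.1, 4.3 | First dressing directly after the operation | No. The arm could be opened before surgery or just after skin closure |
| 4.3.1 | A closed incision before recruitment | Not stated. Read literally, recruitment follows closure, but randomization is not mentioned |
| 5.1 | Consent and eligibility checklist before Day 0 dressing | No. But it allows a patient to count as cleared before the operation |
| 8 | A schedule exists | No |

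Both sequences fit the text: opening the arm once the checklist is done, and opening it after closure. Nothing rules out the first.

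**2. What is still undecided before closure?** Age, consent, allergies, compliance history and type of surgery are known beforehand. Still open are whether the incision is closed, its length against the pad, bleeding, exposed structures, the reference incision (only where there is more than one), closure method and drain use.

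**3. Can eligibility itself depend on the arm?** Yes, through pad size.

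- Avance Solo, Table 2 in Section 3.1: longest pad 30 cm, widest 10 cm.
- Control, size table under Section 3.2: longest pad 25.4 cm, all pads 5.1 cm wide.
- Gap in length: 30 − 25.4 = 4.6 cm.

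With one dressing per incision, a 28 cm incision fits an Avance Solo pad and no listed control pad. If the arm is known, the pad-size exclusion can keep this patient in one arm and remove the same patient from the other. Section 4.4 bars replacement only for patients who were entered and received treatment, so it does not cover a patient allocated but dropped before the dressing. Section 8 names no analysis set.

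**4. Scale.** The plan gives no figure for this point. The nearest is the effect assumed in Section 8, used there for its 162 per arm. The usual formula is

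n = [1.960 √(2p̄(1 − p̄)) + 0.842 √(p₁(1 − p₁) + p₂(1 − p₂))]² / (p₁ − p₂)².

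With 5/30 and 2/30, two-sided, this gives 161 per arm, which agrees with the plan. With the rounded 16% and 8% it gives 258. The point here does not depend on which is used. The assumed difference among 30 patients per arm is (0.16 − 0.08) × 30 = 2.4 patients by the percentages, or 5 − 2 = 3 by the counts.

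**5. Can the bias be sized?** Not from the documents. For a factor with risk ratio R and prevalence q₀ in control and q₁ in the NPWTi arm, with no true device effect and 16% risk in control, the risk in the NPWTi arm is 0.16 × [1 + q₁(R − 1)] / [1 + q₀(R − 1)]. The documents give none of R, q₀ or q₁. On purely assumed values:

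- q₀ = 40%, q₁ = 20%: R = 1.5 gives 0.16 × 1.1/1.2 = 14.7%, a false difference of 1.3 points; R = 3 gives 0.16 × 1.4/1.8 = 12.4%, or 3.6 points.
- q₀ = 50%, q₁ = 10%: R = 1.5 gives 0.16 × 1.05/1.25 = 13.4%, or 2.6 points; R = 3 gives 0.16 × 1.2/2.0 = 9.6%, or 6.4 points.

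The sign reverses if the prevalences are swapped. The spread shows how the mechanism works; it is not an estimate.

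**The case against.** The strongest reply is that Section 4.3.1 already protects the trial: if an incision must be closed before a patient is recruited, closure method is settled by then. An immediate dressing is also compatible with an arm opened after skin closure. A reader might infer from "The 1st dressing will be placed immediately upon completion of the operation" that the arm must be known before closure; the sentence times the dressing and does not support that. This part of the objection stands. It does not close the gap, because no section ties randomization to recruitment or to closure, and Section 5.1 lets the checklist be completed beforehand.

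Other strong readings are also unsupported:

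- *The 24-hour window contradicts immediate application, so another dressing was worn first.* The window is an upper limit, and a dressing placed minutes after closure meets both statements. No section says that entry is delayed.
- *Two or three arm-driven decisions would create or erase the whole expected difference.* That holds only if each decision moves one event. At 16% risk, dropping three typical patients removes 3 × 0.16 = 0.48 expected events, not 2.4.
- *Recording drains and closure as baseline hides an imbalance.* The opposite is true: the data are there and can be tabulated by arm.

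Finally, Section 8 calls the data exploratory and not powered. That limits the consequences but does not answer the point. The pilot is meant to test the assumptions behind a trial of 324, and a bias of this kind does not shrink as numbers grow.

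**Conclusion.** The point holds as a gap in the design that should be closed before enrolment. The arm's opening is neither timed nor concealed, and a site can comply with the plan while final eligibility, reference incision, closure method and drain use follow the arm. The pad-size exclusion is the one place where the documents themselves make eligibility depend on the arm. The chi-squared test in Section 8 cannot repair such differences, and adjusting for choices made after allocation would not restore the randomized comparison.

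The documents do not show that this will happen, in which direction, or by how much. The conclusion rests on the plan's silence about timing and concealment, and on the surgeon making these decisions at or before closure.

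**What to change.** In Sections 4.3, 5.1 and 8, state that:

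- the allocation is concealed and not accessible to the operating surgeon;
- it is opened only after skin closure, and only after the following are recorded: final eligibility, the single reference incision, its length, closure method and drain use;
- pad fit is assessed against the sizes available in both arms. Section 3.2 allows the control product to change, so this should refer to the sizes stocked at the time.

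Report closure method and drain use by arm.

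Separately, the sponsor should reconcile the three statements on the timing and setting of the first application: immediate in 4.3, under 24 hours in 4.3.1, and operating room or hospital bed in 6.1.

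The cost is protocol wording, a short form, a minute or two at the end of surgery, and having both products to hand.

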#### 4.3.1 Inclusion Criteria

The following criteria must be met before a patient is recruited to the evaluation:

- The patient must be at least 18 years of age
- Males and females provided they are not pregnant and if of reproductive age are using contraception.
- Have a closed surgical incision post-surgery/closure (<24 hours after).
- The patient is able to understand the evaluation and is willing to consent to the evaluation.
- Undergoing appropriate: wound "high risk" surgery
- Foot and ankle surgery
- Vascular groin incision
- Long leg vein harvest incision
- · Closed forefoot and major amputation surgery
- Breast augmentation and reduction surgery
- Patient on metabolic agent, immunosuppressants, or steroid therapy will not be excluded from this study

# 4.3.2 Exclusion Criteria

- Incisions in excess of effective dressing pad size provided.
- Patients with a known history of poor compliance with medical treatment.
- Patients who have participated in this trial previously and who were withdrawn.
- Patients with known allergies to product components (silicone adhesives and polyurethane films (direct contact with incision), acrylic adhesives (direct contact with skin), polyethylene fabrics and super-absorbent powders (polyacrylates) (within the dressing).
- Incisions where daily inspection is required underneath the dressing.
- Incisions which have an infection which is not being treated with systemic antibiotics.
- Incisions which are actively bleeding.
- Exposure of blood vessels, organs, bone or tendon at the base of the reference incision.

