#### 4.4 WITHDRAWAL

Any patient who interrupts the evaluation treatment for longer than 3 days will be withdrawn from the evaluation.

Patients who do not respond to therapy should be withdrawn from the evaluation only at the point where it becomes necessary to change the treatment on clinical grounds.

Patients may drop out or be withdrawn for the following reasons:-

- at their own request\*
- at the discretion of the clinician (because of lack of response, an adverse incident, poor compliance etc.).
- as their incision is no longer suitable for treatment with Avance® Solo
- \* Although patients need not give a reason for requesting withdrawal from the evaluation, the Clinician should make a reasonable effort to ascertain the reason(s), while fully respecting the patient's rights.

Patients who drop out or who are withdrawn from the evaluation will not be replaced if they have been entered onto the study and have received evaluation treatments.

Patients who drop out or who are withdrawn or whose wound heals will not be reentered into the evaluation at a later date.

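### The incision-size limit names no arm, and incisions over 25.4 and up to 30 cm fit a listed Avance pad but no listed control pad

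*Combined protocol and SAP*

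**What the plan says.** Incision size is limited in two places. Section 4.3.2 excludes "Incisions in excess of effective dressing pad size provided". Section 4.3 says that the reference incision "will be an incision which fits the dressing sizes included". Neither sentence names a product or an arm. Section 4.3 also opens with "Patients with an incision deemed suitable for treatment with Avance® Solo or HAAMPOD will be screened against the inclusion and exclusion criteria", where the link between the two products is *or*.

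The sizes are listed product by product:

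- **Avance.** Section 3.1 introduces Table 2 with "The dressing and pad sizes that will be used for the closed incision wounds in this study are listed below". Its caption is "Table 2: Dressing sizes to be used in the study", and it holds Avance sizes only. The effective pads are 5 x 15, 5 x 25, 5 x 30, 10 x 15 and 10 x 25 cm.
- **Control.** The list under Section 3.2 has three pads, all 5.1 cm wide: 15.2, 20.3 and 25.4 cm long. The largest is "5.1 cm x 25.4 cm". Section 3.2 adds that the control product may change with hospital purchasing contracts.

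Section 4.3 also states "Only 1 dressing per incision must be used on an incision", so two control dressings cannot be combined on a longer incision.

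**The concern.** In a randomised comparison, a patient should be eligible or ineligible whichever arm is drawn. Here the listed sizes and the one-dressing rule together leave a range of lengths that only one arm can treat.

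Four features of the plan make this matter:

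- The trial is open label (Section 2.1).
- Section 8 allocates from a computer-generated list but does not say when an assignment becomes known.
- The first dressing goes on as soon as the operation ends, and a patient with several incisions contributes the biggest or the best suited one (Section 4.3). A clinician who knows the arm could therefore settle on a different reference incision in each arm.
- Section 8 defines no analysis population, so nothing says how a randomised control patient with no fitting dressing would be handled.

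What is at stake is whether the two groups are comparable on incision length, a feature that may be related to the primary outcome. Section 8 presents the study as a pilot to check the assumptions behind a 324-patient trial. A control complication rate taken from a differently selected group would serve that purpose poorly, and a larger sample would not correct it.

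**Working it through.** **Inputs.** Avance pads from Table 2 (Section 3.1); control pads from the list under Section 3.2; one dressing per incision (Section 4.3).

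**Step 1: reproduce the listed areas (width x length).**

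- Avance: 5 x 15 = 75, 5 x 25 = 125, 5 x 30 = 150, 10 x 15 = 150 and 10 x 25 = 250 cm². All agree with Table 2.
- Control: 5.1 x 15.2 = 77.52, 5.1 x 20.3 = 103.53 and 5.1 x 25.4 = 129.54 cm². These agree with the stated 77.5, 103.5 and 129.5.

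The dimensions are therefore internally consistent and can be relied on.

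**Step 2: fit check.** An incision fits an arm if at least one single listed pad is at least as long and as wide. For a narrow linear incision:

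| Length (cm) | Fits an Avance pad | Fits a control pad |
|---|---|---|
| 25 | yes | yes |
| 25.4 | yes | yes |
| 26 | yes | no |
| 28 | yes | no |
| 30 | yes | no |
| 31 | no | no |

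The one-arm window runs from just over 25.4 cm up to 30 cm: 30 - 25.4 = 4.6 cm.

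**Step 3: apply the rules as written to a 28 cm incision.** It does not exceed the longest pad in Table 2, which the protocol presents as the study sizes, so neither Section 4.3 nor Section 4.3.2 clearly excludes it. If the patient is allocated to control, no listed pad covers the incision and a second dressing is not allowed.

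**Step 4: direction if such patients left the control arm.** Let p be the overall complication rate with no treatment effect, f the fraction of incisions in the window, and r their complication rate. The control rate after dropping them is (p - f·r)/(1 - f), which is below p whenever r is above p. Control would then look better than it should, to the disadvantage of Avance. The documents give neither f nor r, so no value can be put on this.

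**Step 5: yardstick.** With 30 per arm and the 16% rate from Section 8, the standard error of the difference under no effect is sqrt(2 x 0.16 x 0.84 / 30) = sqrt(0.00896) = 0.095, about 9.5 percentage points. Chance variation in this pilot is large.

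**The case against.** The strongest reply is that the unnamed limit can be read as the sizes common to both products, since both lists sit in Section 3. On that reading there is no imbalance. Also, Section 4.3.1 wants the criteria met before recruitment, and the table in Section 5.1 puts the eligibility checklist ahead of the first dressing. Both observations are fair, and they limit the point to an undefined rule. They do not remove it. No sentence requires a fit to both products, Table 2 points the other way, and the incision exists only after surgery, with nothing tying its measurement to a time before the arm is known.

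A reader might infer more than the documents support:

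- **That long incisions will be removed from control after allocation.** The plan does not provide for this. It only fails to prevent it.
- **That such patients would be replaced.** Section 4.4 says that patients who leave "will not be replaced if they have been entered onto the study and have received evaluation treatments". It is silent on patients who were never treated, and silence is not permission.
- **That pad width and area matter as much as length** (10 v 5.1 cm; 250 / 129.5 = 1.93 times the area). These are closed, essentially linear incisions. Section 6.1 records only their length, and no pad width or margin is required.
- **That amputation and breast incisions are affected.** No incision sizes are given for any procedure. Long leg vein harvest is suggestive by its description only.
- **That the bias has a known size.** Any figure would rest on an invented fraction and an invented complication rate. Section 8 also calls the data exploratory and not powered for significance.

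**Conclusion.** The point holds as a gap in the eligibility rule. On the listed sizes, and with one dressing per incision, incisions over 25.4 and up to 30 cm can be accepted on a literal reading yet cannot be covered in the control arm. With open-label treatment and no stated time for opening the allocation, exclusion or choice of reference incision can come to depend on the arm.

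The certain part is the 4.6 cm difference in maximum pad length. The number of patients affected among the planned 60 (2 x 30) cannot be computed, and it may be small. A bias against Avance follows only under two assumptions: that unfitted control patients are dropped, and that longer incisions have more complications. The documents establish neither. This is worth correcting before enrolment because the correction is cheap. It does not show that the comparison will be biased.

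**What to change.** Replace the size exclusion in Section 4.3.2 with: *Reference incision that cannot be fully covered by a single listed dressing of each of the two study products (on current sizes, longer than 25.4 cm; update the limit if the control product changes).* The wording should make clear that the incision must fit both products; a phrase such as *either product* would bring the ambiguity back. Align the matching sentence in Section 4.3.

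Add that the reference incision is selected, measured and recorded before the allocation is opened. Length is already a baseline item in Section 6.1, so this needs only one checklist entry and a stated order of steps.

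Alternatively, reconcile the two size lists so that both arms cover the same range of lengths.

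The cost is one line of text and one checklist item. The downside is that a few very long incisions become ineligible, and on the current sizes these are incisions that the control arm could not cover in any case.
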